3.1.2 Optional Tolvaptan Treatment Component

Subjects enrolled in the 6-month core safety follow-up component may be eligible to receive optional tolvaptan treatment for their hyponatremia. Eligibility criteria for optional tolvaptan treatment are outlined in [Appendix 5](#). Eligibility for optional tolvaptan treatment must be determined at the pre-treatment baseline visit (Day -4 to Day -1) of each dosing cycle. Eligible subjects can be treated at any time with optional tolvaptan during the 6-month core safety follow-up component. Optional tolvaptan treatment duration will be case-specific; it can be short-term or long-term, and consist of 1 or more treatment cycles. When a cycle with optional tolvaptan treatment is completed, including the Follow-up Phase visits, subjects will continue in the core safety component to complete the remainder of visits until Month 6. Within this trial, tolvaptan treatment will not extend beyond the 6-month core safety trial period. If the subject completes the 6-month core safety component while on optional tolvaptan treatment, the subject will complete the Month 6 core safety component visit, terminate treatment, and immediately enter the Follow-up Phase.

If a subject simultaneously participates in both core safety and optional tolvaptan treatment components, the visit days will be calculated between both components to ensure the assessments can be overlapped, where applicable.

3.1.2.1 Treatment Interruption on Day 30

Thirty days after the start of optional tolvaptan treatment, subjects will interrupt treatment for up to 2 doses (Days 31-32). The need for continuing treatment after this tolvaptan interruption will be assessed at minimum once daily (or more as needed) during this time.

Subjects who are expected to receive tolvaptan for greater than 30 days duration should demonstrate the need for continued treatment by discontinuing tolvaptan for up to 2 consecutive doses while undergoing close monitoring of serum sodium levels.

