However, there is a subgroup of subjects who have an identifiable cause for hyponatremia that has not (or cannot be) changed that will have an option to be excused from this brief interruption of tolvaptan. Examples of such causes include concomitant treatment for refractory seizures with a hyponatremia-inducing medication such as oxcarbazepine (which can increase vasopressin production by the pituitary) that cannot be changed or discontinued, or subjects with a known underlying hyponatremia inducing condition such as volume overload from a failing Fontan repair.

During this treatment interruption, subjects will have serum sodium levels monitored closely. Subjects who demonstrate a decline in serum sodium level will be restarted at the prior dose of tolvaptan as per clinician judgment. Subjects whose serum sodium declines ≥ 4 mEq/L (mmol/L) or who exhibit symptoms of hyponatremia will be immediately placed under direct observation as per clinician judgment and will be restarted at their previous dose of tolvaptan unless there is a compelling reason to reduce the dose. Subjects will be closely monitored until stable.

Investigators should consider the overall clinical status of the subject (including underlying etiology of hyponatremia and volume assessment), prior response to tolvaptan, concomitant medications, age, and weight when determining the appropriate dose at which to restart a subject after a brief discontinuation of tolvaptan to assess the need for further treatment. Investigators should discuss any concerns with the medical monitor.

- Subjects who resume dosing within 72 hours post last dose (either on Day 32 or by the morning of Day 33), can do so at the same dose or a lower dose without having to go through the full titration cycle again.
- Subjects who have a dosing interruption of ≥ 72 hours must enter a new treatment cycle and repeat the full titration cycle in a hospital setting.
- Subjects who do not need to continue treatment with tolvaptan will proceed directly to the Follow-up Phase (Day 7 Follow-up). Subjects will then continue in the core safety follow-up component and complete remaining required visits, as applicable.

The optional tolvaptan treatment component of the trial will be available for the 6-month duration of the core safety component for each subject.

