3.2.1 Optional Tolvaptan Treatment

3.2.1.1 Tablet Formulation

Tolvaptan tablets will be administered orally once daily (QD), preferably in the morning hours, with a dose-proportional amount of water. Doses of ≥ 15 mg of tolvaptan will be given with 240 mL of water, 7.5 mg of tolvaptan will be given with 120 mL of water, and 3.75 mg of tolvaptan will be given with 60 mL of water. The quantity of water ingested with each dose should be recorded.

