3.5.2.3 Pharmacokinetic Variable: Optional Tolvaptan Treatment Component

- Plasma concentrations of tolvaptan and metabolites in subjects who have continued tolvaptan therapy for 8 consecutive weeks

One PK sample should be taken after 8 weeks of continuous treatment per cycle. This may include a discontinuation of < 72 hours (up to 2 doses) during the Day 30 treatment interruption.

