3.7.2 Optional Tolvaptan Treatment Component

If a subject has a clinical need for tolvaptan, the subject may be screened for eligibility to be treated with tolvaptan (see [Appendix 5](#)). To assess the subject's eligibility to receive tolvaptan, the subject must have been off treatment with IMP for 7 days following the end of treatment in the previous tolvaptan trial.

Subjects who meet the eligibility criteria for tolvaptan treatment will be administered tolvaptan based on age, weight, and the use of CYP3A4 inhibitors on Day 1 of the cycle. Subsequent dosing adjustments are based on serum sodium response. Refer to [Section 3.2.1.2](#) for dosing guidelines.

Trial assessments and time points for the optional tolvaptan treatment component are summarized in [Table 3.7.2-1](#) and described in [Section 3.7.3.2](#).

Table 3.7.2-1 Schedule of Assessments for Each Treatment Cycle																	
Procedures^a	Pre-treatment Baseline^b	Titration Phase^b			Post-titration						Treatment Cycle Month 2	Treatment Cycle Month 3+ (Maintenance)	Month 6 (D173) Cycle DC (+ 2 wk)	Follow-up Phase^k			
		Day 1	Day 2 and 3	Day 4	Day 7, 14 and 21	Day 30 (±1)	Day 31^c	Day 32^c	Day 33^c	Day 34^c				24 (±4) hours post-last dose	7 (±1) days post-last dose	14 (±2) days post-last dose	
	Days -4 to -1										every 2 weeks (±2 days) Mth 2 Wk 2 (D47), Mth 2 Wk 4 (D61)	Once monthly (±2 days) Mth 3 (D89), Mth 4 (D117), Mth 5 (D145)					
Review eligibility criteria for treatment	X																
Vital signs	X	X	X	X	X	X	X	X	X	X	X	X	X	X	X	X	
Physical examination ^d	X											X	X				
Body height and weight/ growth percentiles	X											X	X				
Pregnancy test ^e	X								X		X	X		X			
Clinical status assessment	X						X	X	X	X	X	X					
Neurological assessment ^f	X						X	X	X	X	X	X					
Quality of Life assessment	X											X					
Assess ALT, AST, BT, and creatinine	X					X					X ^g	X	X	X			
Assess serum sodium ^h	X	X	X	X	X	X	X	X	X	X	X	X	X	X	X	X	

- ^bTitration can be up to 4 days. Cycles can be repeated as needed during the 6-month core safety component. If a subject is off tolvaptan treatment for ≥ 72 hours, titration/reinitiation of tolvaptan will require reassessment of eligibility criteria and will begin in a hospital setting as part of a new treatment cycle.
- ^cDuring the Day 30 treatment interruption, Days 31, 32, 33 and 34 must follow consecutively. Once the Day 30 visit is determined, the subsequent visit days do not have a window.

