3.7.3.2.2 Titration Phase

A subject who requires tolvaptan treatment can be treated for as many cycles as deemed necessary by the investigator within the 6 month trial period. The duration of treatment cycles may vary per the investigator's assessment of clinical need. Regardless of the number of treatment cycles and the duration of tolvaptan treatment in each cycle, optional tolvaptan treatment cycles will consist of a titration phase, a maintenance phase, and a follow-up phase. The schedule of assessments for the optional tolvaptan treatment component is shown in [Table 3.7.2-1](#).

The first dose of tolvaptan will be administered upon successful completion of all pretreatment baseline procedures. Subjects will enter a titration phase and follow the titration schedule outlined in [Section 3.2.1.2](#). Subjects will be required to be in a hospital setting during initiation and titration of tolvaptan.

During the Titration Phase on Day 1 up to Day 4 of treatment, in addition to serum sodium samples obtained for treatment qualification and efficacy endpoints, supplemental samples for the purposes of safety assessment will be obtained using a point of care (POC) sodium assessment unit, where available, at 4 to 6 (+0.25) hours postdose and at 18 (\pm 1) hours postdose. A POC assessment unit is preferred; however, regular blood draws may be used (especially if they can be combined with standard of care labs). A schedule of blood samples required for serum sodium assessments can be found in [Table 3.7.4.1.2-1](#).

3.7.3.2.2.1 Day 1

All titration of tolvaptan will be done in a hospital setting. Please see [Section 3.2.1](#) for details on titration and dosing.

The following procedures will be performed on Day 1:

- 1) Vital signs (blood pressure, heart rate, respiratory rate, and temperature) will be assessed after the subject has been supine for \geq 3 minutes. Vital signs should be assessed prior to blood draws.
- 2) A blood sample for STAT serum sodium testing will be collected within 2 to 4 hours prior to the first dose. Results need to be reviewed prior to dosing to confirm continued treatment eligibility of the subject.

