3.7.3.2.4 Day 30 Interruption: 30 (± 1) Days Post-first Dose

After 30 days of tolvaptan treatment, all subjects (exceptions explained in [Section 3.1.2.1](#)) should discontinue treatment for up to 2 doses to assess the continued need for tolvaptan treatment. Subjects should arrive to the clinic prior to taking the morning dose of tolvaptan.

The following assessments will be performed during the Day 30 visit:

- 1) Vital signs (blood pressure, heart rate, respiratory rate, and temperature) will be assessed after the subject has been supine for ≥ 3 minutes. Vital signs should be assessed prior to blood draws.
- 2) A blood sample for serum sodium testing must be assessed at 24 (± 4) hours post-last dose with the results reviewed prior to subsequent tolvaptan dosing.
- 3) A blood sample for ALT, AST, BT, and creatinine will be collected.
- 4) Tolvaptan dispensed the previous week will be returned for accountability.
- 5) Tolvaptan will be administered during the clinic visit.
- 6) Concomitant medications will be recorded.
- 7) Adverse events will be assessed.

- 8) Instruct subjects to return to the clinic for visits on Day 31 and 32.

3.7.3.2.4.1 Day 31

The following assessments will be performed:

- 1) Vital signs (blood pressure, heart rate, respiratory rate, and temperature) will be assessed after the subject has been supine for ≥ 3 minutes. Vital signs should be assessed prior to blood draws.
- 2) A clinical status assessment will be performed. If the subject has any positive findings on the clinical status assessment, a full neurological examination can be performed per investigator judgment.
- 3) A blood sample will be collected for serum sodium testing at 24 hours (± 4 hours) post the Day 30 dose. Refer to [Figure 3.1-1](#) for a trial schematic, and [Section 3.2.1](#) for a description of the treatment continuation decision.
- 4) Concomitant medications will be recorded.
- 5) Adverse events will be assessed.

3.7.3.2.4.2 Day 32

The following assessments will be performed:

- 1) Vital signs (blood pressure, heart rate, respiratory rate, and temperature) will be assessed after the subject has been supine for ≥ 3 minutes. Vital signs should be assessed prior to blood draws.
- 2) A clinical status assessment will be performed. If the subject has any positive findings on the clinical status assessment, a full neurological examination can be performed per investigator judgment.

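### The two-dose interruption at Day 30 ends exactly on the 72-hour new-cycle cut-off, and the Day 33 sodium window falls on both sides of it

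*Protocol*

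**What the plan says.** - **Dosing interval.** Protocol Section 3.2.1.1: tablets are "administered orally once daily (QD), preferably in the morning hours".
- **Last dose before the interruption.** Section 3.7.3.2.4, Day 30: "Tolvaptan will be administered during the clinic visit". Section 3.1.2.1 then has the child miss up to two doses, those of Days 31 and 32.
- **Two restart rules.** Section 3.1.2.1 lets a child resume at the same or a lower dose, without full titration, "within 72 hours post last dose (either on Day 32 or by the morning of Day 33". The next bullet reads: "Subjects who have a dosing interruption of ≥ 72 hours must enter a new treatment cycle and repeat the full titration cycle".
- **The plan's own reading of two missed doses.** Section 3.5.2.3, on eight weeks of continuous treatment: "This may include a discontinuation of < 72 hours (up to 2 doses) during the Day 30 treatment interruption".
- **Day 33 visit.** Section 3.7.3.2.4.3, item 4, and Table 3.7.4.1.2-1 place the sodium sample at 72 h after the Day 30 dose, plus or minus 4 h. Item 5a doses a child off drug for less than 72 h. Item 5b sends a child off drug for 72 h or more to a new cycle.
- **Visit days.** Table 3.7.2-1, footnote c: "Once the Day 30 visit is determined, the subsequent visit days do not have a window". Only the hour can move.

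**The concern.** The plan means a child who misses both doses and still needs tolvaptan to restart on the morning of Day 33 within the current cycle. Run at its nominal times, the schedule puts that restart on the cut-off for leaving the cycle. The sodium sample listed immediately before the restart decision is centred on the same instant.

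The two branches differ a great deal. Below 72 h, a decline in sodium is enough to resume, and Section 3.1.2.1 says a child whose sodium falls by 4 mEq/L or more will be restarted. At 72 h or more, the child must requalify with sodium below 130 mEq/L (Section 3.3.2; Appendix 5, eligibility criterion 3) and be retitrated in hospital.

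For illustration, take a child whose sodium falls from 138 to 132 mEq/L at the Day 33 draw. The fall is 6 mEq/L, so Section 3.1.2.1 restarts the child. The value is not below 130, so under Section 3.3.2 the child is ineligible at that time. Which rule applies depends on the clock.

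The branch also affects the analysis. SAP Section 5.1.6.2 takes the primary-endpoint baseline afresh at each cycle, and the eight-week pharmacokinetic clock starts again.

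**Working it through.** **Inputs.** Dosing interval 24 h (Section 3.2.1.1); time zero is the Day 30 clinic dose (Section 3.7.3.2.4); two doses skipped (Section 3.1.2.1); cut-off at 72 h or more (Section 3.1.2.1 and Section 3.7.3.2.4.3, item 5b); Day 33 sample at 72 ± 4 h (Section 3.7.3.2.4.3, item 4, and Table 3.7.4.1.2-1).

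**1. When the next dose falls due.** Time = (doses skipped + 1) × 24 h.
- One skipped: 2 × 24 = 48 h (Day 32).
- Two skipped: 3 × 24 = 72 h (Day 33). This reproduces the plan's nominal Day 33 sample time.

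**2. Which rule applies at exactly 72 h.** Read as no more than 72 h, the resumption bullet is satisfied. The new-cycle bullet is satisfied too. Section 3.1.2.1 therefore classifies the child both ways, Section 3.5.2.3 counts two missed doses as less than 72 h, and item 5b sends the child to a new cycle.

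**3. The sample window.** 72 − 4 = 68 h to 72 + 4 = 76 h, 8 h in all. The part at or after the cut-off is 76 − 72 = 4 h, half of the window.

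**4. Draw times that still allow an in-cycle restart if the site waits for the result.** With a turnaround of *t* hours, the draw must come before 72 − *t*, so usable time = (72 − *t*) − 68. The plan gives no turnaround; the values below are assumptions.

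| Turnaround (h) | Usable draw time (h of 8) |
|---|---|
| 0 | 4 |
| 1 | 3 |
| 2 | 2 |
| 4 | 0 |

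These are hours of window, not proportions of children.

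**5. Delay once past the cut-off.** The delay is not fixed. Appendix 5, ineligibility criterion 11, bars tolvaptan within 4 days of the qualifying sodium values. Read literally, the first qualifying value comes no earlier than 4 × 24 = 96 h, the second at 96 + 12 = 108 h, and the dose at 108 + 2 = 110 h. That is a lower bound, and it arises from a separate rule that applies to any child past 72 h. If any pretreatment sodium is 130 mEq/L or more, there is no restart at that time.

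**The case against.** The best reply is that a site can obey every rule as written. The ± 4 h applies to the sample and not to the dose, morning dosing is only preferred, and items 5a and 5b divide cleanly at 72 h. A draw at 68 to 70 h with a prompt result keeps the child in the cycle. Need is reviewed at least daily, with sodium also taken at 24 and 48 h, so many children with a clear decline would restart on Day 32. The Day 33 section does not require the result before the dose, whereas the Day 34 section does, so a child whose need was already clear could be dosed without it. On this view the conflict reaches mainly children whose need is accepted only on Day 33, and stricter requalification for them is defensible.

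Much of this stands. New-cycle entry is not inevitable, the turnaround figures are conditional, and children excused from the interruption are unaffected. The medical monitor and rescue therapy remain available.

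The conflict itself is not answered. Items 5a and 5b settle the overlap by excluding from the cycle a child that Sections 3.1.2.1 and 3.5.2.3 keep in it. Nothing tells a site to use only the first half of the sample window. If stricter requalification for late responders were intended, Section 3.1.2.1 would not offer Day 33 as a restart day.

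**Conclusion.** The concern holds as a defect in the plan that should be corrected. Two skipped once-daily doses bring the next dose to exactly 72 h, where adjacent bullets give opposite instructions, and half of the permitted Day 33 sample window lies at or past the cut-off. The further loss of usable time, down to none at a 4 h turnaround, rests on the site waiting for the Day 33 result and on an assumed turnaround.

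Two limits apply. Figure 3.1-1, to which the Day 33 section refers for the continuation decision, and the dosing row of the current Table 3.7.2-1 are not visible in the text available. SAP Section 5.1 states that no subject received optional tolvaptan, so no reported result changes.

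**What to change.** 1. In Section 3.7.3.2.4.3, item 4, and the Day 33 row of Table 3.7.4.1.2-1, replace the 72 ± 4 h timing with a STAT sodium at 68 to 70 h after the Day 30 dose. Require the result to be reviewed, and any restart dose to be given, before 72 h. This is the plan's own Day 1 rule ("A blood sample for STAT serum sodium testing will be collected within 2 to 4 hours prior to the first dose", with the result reviewed first) counted back from the cut-off: 72 − 4 = 68 h and 72 − 2 = 70 h.
2. In Section 3.1.2.1, change the resumption rule to less than 72 h, so that the two bullets no longer overlap.
3. Advise sites to time the Day 30 dose so that the Day 33 draw is workable. A dose at 11:00 puts 68 h at 07:00, 70 h at 09:00 and 72 h at 11:00 on Day 33. For a child usually dosed at 08:00, the Day 30 pre-dose sample at 24 ± 4 h may be drawn from 04:00 to 12:00, so an 11:00 dose fits.

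**Cost.** Two timing edits and one wording edit. The new draw time lies inside the 68 to 76 h already permitted, so no samples, visits or patients are added, and the in-hospital rule at 72 h or more is kept. The draw window narrows from 8 h to 2 h and falls 2 to 4 h earlier on the clock than the Day 30 dose. Without the timing advice, a child dosed at 08:00 on Day 30 would need a draw at 04:00 to 06:00 on Day 33. The result must be back in under 4 h for a draw at 68 h and under 2 h for a draw at 70 h; a site that cannot manage this would still miss the cut-off.

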3.2 Trial Treatments

The core safety follow-up component of the trial does not contain any trial specific treatments. However, eligible subjects have the opportunity to receive tolvaptan treatment in the optional tolvaptan treatment component.

3.2.1 Optional Tolvaptan Treatment

3.2.1.1 Tablet Formulation

Tolvaptan tablets will be administered orally once daily (QD), preferably in the morning hours, with a dose-proportional amount of water. Doses of ≥ 15 mg of tolvaptan will be given with 240 mL of water, 7.5 mg of tolvaptan will be given with 120 mL of water, and 3.75 mg of tolvaptan will be given with 60 mL of water. The quantity of water ingested with each dose should be recorded.

3.2.1.2 Titration Guidelines for the Optional Tolvaptan Treatment Component

In the optional tolvaptan treatment component of the trial, eligible subjects will receive tolvaptan based on age, weight, and the use of CYP3A4 inhibitors. Tolvaptan tablets will be administered orally QD, preferably in the morning hours.

Tolvaptan doses can be titrated QD and will be based on serum sodium levels assessed at 24 (\pm 4) hours following initiation of therapy and each subsequent dose. Titration guidelines are detailed in [Figure 3.2.1.2-1](#). Titration must occur in a hospital setting. Titration may not occur within 24 (\pm 4) hours of the previous dose and must be based on serum sodium assessment obtained $>$ 20 hours post previous dose. Titration is limited to no more than twice the previous dose, and will be limited to the maximum dose per body weight.

An age-appropriate formulation is not available for this trial. Therefore, the following subjects will be excluded from the optional treatment component of this protocol:

- Subjects $<$ 4 years of age, or weighing $<$ 10 kg,
- Subjects with an inability to swallow tablets, and
- Subjects weighing $<$ 20 kg and taking a moderate or potent CYP3A4 inhibitor

[Table 3.2.1.2-1](#) outlines starting tolvaptan doses and adjustments when tolvaptan is administered concurrently with potent or moderate CYP3A inhibitors. Tolvaptan doses will be reduced 75% and 50% if a potent or moderate inhibitor, respectively, is being concurrently administered.

Table 3.2.1.2-1 Starting Tolvaptan Doses With or Without Potent or Moderate CYP3A4 Inhibitors				
Age/Weight	Can subject swallow a tablet?	Starting Dose: No CYP Inhibitor	Starting Dose: Moderate CYP Inhibitor	Starting Dose: Potent CYP Inhibitor
≥ 4 y AND ≥ 10 to < 20 kg	Yes	3.75 mg	Not eligible for treatment	Not eligible for treatment
≥ 4 y AND ≥ 20 to ≤ 50 kg	Yes	7.5 mg	3.75 mg	Not eligible for treatment
≥ 4 y AND > 50 kg	Yes	15 mg	7.5 mg	3.75 mg

Based on the weight versus dose information provided in [Table 2.2-1](#) and taking into consideration the concomitant use of a CYP3A4 inhibitor, the starting doses are as follows:

Subjects ≥ 4 years of age and weighing ≥ 10 to < 20 kg:

- Not taking a moderate or potent CYP3A4 inhibitor will receive a QD oral tolvaptan tablet dose of 3.75 mg, with possible up-titration to 7.5 mg and 15 mg
- Taking a moderate or potent CYP3A4 inhibitor are not eligible for optional tolvaptan treatment

Subjects weighing ≥ 20 to ≤ 50 kg:

- Not taking a moderate or potent CYP3A4 inhibitor will receive a QD oral tolvaptan tablet dose of 7.5 mg, with possible up-titration to 15 mg and 30 mg
- Taking a moderate CYP3A4 inhibitor will receive half the starting tolvaptan tablet dose, eg, 3.75 mg tablet, with possible up-titration to 7.5 mg and 15 mg.
- Subjects are not eligible to receive optional tolvaptan treatment if they are taking a potent CYP3A4 inhibitor.

Subjects weighing > 50 kg

- Not taking a moderate or potent CYP3A4 inhibitor will receive a QD oral tolvaptan tablet dose of 15 mg, with possible up-titration to 30 mg and 60 mg
- Taking a moderate CYP3A4 inhibitor will receive half the starting tolvaptan tablet dose, ie, 7.5 mg, with possible up-titration to 15 mg and 30 mg

- Taking a potent CYP3A4 inhibitor will receive one quarter the starting tolvaptan tablet dose, eg, 3.75 mg, with possible up-titration to 7.5 mg and 15 mg.

Subjects not eligible for the optional tolvaptan treatment component still remain eligible for the core safety follow-up component.

Subjects eligible for the optional tolvaptan treatment component will titrate according to the guidelines listed in [Figure 3.2.1.2-1](#), targeting a final serum sodium concentration between 135 and 140 mEq/L (mmol/L). The clinician-directed target range is also acceptable.

Treatment can be discontinued at any time and cycles may be repeated as needed. If subjects are off tolvaptan treatment for ≥ 72 hours, re-initiation of tolvaptan treatment, starting with the pre-treatment baseline visit will occur. This will require a reassessment of the eligibility criteria, a tolvaptan titration period, and will begin in a hospital setting as part of a new treatment cycle.

The titration scheme is shown in [Figure 3.2.1.2-1](#).

[figure not shown]

Figure 3.2.1.2-1 Titration Scheme

Titration guidelines are designed to ideally achieve a change in serum sodium concentration of at least 4 to 8 mEq/L (mmol/L) /24 hours but not \geq 12 mEq/L (mmol/L)/24 hours.

Tolvaptan dose titration (after the initial dose) must be based on changes in serum sodium levels as follows:

- If the serum sodium level increases by \leq 4 mEq/L (mmol/L)/24 hours and the subject is still below the therapeutic target for serum sodium level (135 mEq/L [mmol/L]), then the tolvaptan dose may be titrated up to the next scheduled dose.
- If the serum sodium level increases $>$ 4 to \leq 8 mEq/L (mmol/L)/24 hours in response to tolvaptan treatment and the serum sodium is \leq 140 mEq/L (mmol/L), then the dose of tolvaptan should remain the same for the subsequent day.
- If the serum sodium level increases $>$ 8 mEq/L (mmol/L)/24 hours or reaches a concentration of $>$ 140 mEq/L (mmol/L), then the next dose of tolvaptan should not be given and the medical monitor should be contacted to consider options (ie, down-titration, tolvaptan discontinuation, concomitant medication adjustment, fluid supplementation and/or withdrawal).
- If serum sodium level increases by \geq 12 mEq/L (mmol/L) in the 24 hour period following dosing, or, at any time after dosing, the serum sodium level is $>$ 145 mEq/L (mmol/L), the next dose of tolvaptan should not be given and the medical monitor should be contacted immediately to consider options.

